4.2 Inclusion Criteria

1. Male and female patients aged ≥ 6 years and ≤ 65 years on the day informed consent is obtained
2. Patients diagnosed with TSC based on the clinical diagnostic criteria of International Tuberous Sclerosis Complex Consensus Conference 2012 and presenting visible facial angiofibroma
3. An FA severity score of 2 or 3 on the IGA scale
4. Patients or their legal representatives capable of understanding the explanation of the clinical trial and who give written informed consent for participation
5. Patients or their legal representatives able to maintain patient diaries following the instructions of the investigator or sub-investigator

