4.3 Exclusion Criteria

1. Patients who cannot carry out the treatment plan or follow-up assessment
2. Patients with serious skin lesions such as erosions or ulcers
3. Patients with known hypersensitivity to any component of the study product
4. Patients who have received rapamycin/sirolimus, everolimus, or temsirolimus within 3 months of enrolment
5. Patients who received laser therapy or surgical therapy within 6 months prior to trial enrolment
6. Patients who participated in any other clinical trial within 3 months prior to the day of enrolment
7. Patients judged unsuitable for this clinical trial by the investigator or sub-investigator
8. Pregnant or lactating females
9. Sexually active females of childbearing potential not using adequate contraception and sexually active males not using adequate contraception*
10. Patients with immune dysfunction or receiving any form of immunosuppression
11. Patients with severe FA, with a score of 4 on the IGA scale
12. Patients with an FA severity score of less than 2 on the IGA scale

*Methods of contraception that are deemed adequate have failure rates of $< 1\%$, including: established use of oral contraceptives in conjunction with a barrier method of contraception, injected or implanted hormonal methods of contraception; placement of intrauterine device (IUD) or intrauterine system (IUS); barrier methods of contraception including condom and/or occlusive cap (diaphragm or cervical/vault caps) with spermicidal foam/gel/film/cream/suppository; sexual abstinence; hysterectomy; post-menopausal; sterilized; vasectomy.

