6 STUDY DATA AND ENDPOINTS

6.1 Efficacy data

6.1.1 Primary Efficacy Endpoint

At screening, each visit (V1-V5) and at follow-up a blinded dermatologist will grade each patient's lesion using the Investigator's Global Assessment (IGA) of facial angiofibroma severity developed by the sponsor and created solely to identify the response of a treatment in FA associated with TSC.

Table 2: IGA scoring of Facial Angiofibroma Lesions

Grade	Short Description	Detailed Description
0	Clear	No signs of facial angiofibroma
1	Almost Clear	Few small angiofibromas (< 2 mm); normal to pink coloration in affected area*
2	Mild	Predominantly small angiofibromas (< 2 mm) with few intermediate tumors (2-4 mm); pink to red coloration in affected area
3	Moderate	Predominantly intermediate angiofibromas (2-4 mm) with few large tumors (> 4 mm); red coloration in affected area
4	Severe	Mix of intermediate (2-4 mm) and large angiofibromas (>4 mm) present diffusely on face; intense and generalized redness on the whole face

* Note: coloration refers to both the FA lesions and the background facial skin tone
Where lesion size and coloration are discrepant within the grade, emphasis should be placed on lesion size.

The primary efficacy endpoint is the percentage of patients obtaining successful treatment, based on the blind assessment using the IGA scale after 26 weeks or at discontinuation/withdrawal. Success is defined as clear or almost clear with an improvement of at least two grades from baseline, i.e. 2 to 0; 3 to 1.

To the extent possible, the same Investigator should conduct all IGA assessments per patient at each site throughout the study.

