7 EXPERIMENTAL PROCEDURE

The study is intended to be carried out over a total of up to 10 months. The study consists of a Screening Phase (up to 3 months), a Treatment Phase (baseline and 5 clinical visits; 6 months), and Follow-Up (1 month). For early withdrawals, the follow-up visit will be scheduled from the last visit where subject withdrawal was confirmed. The study assessments are summarized in Table 3.

Table 3: Schedule of Assessments

Assessment	Screening Phase			Treatment Phase						Follow-Up
	Informed consent	Screening	Randomization	V0 Baseline	V1 2 weeks	V2 8 weeks	V3 14 weeks	V4 20 weeks	V5 26 weeks	4 weeks after final dose
Tolerance	≤3 months before V0	≤14 days before V0		NA	±3 days	±3 days	±3 days	±3 days	±3 days	±5 days
Informed consent	X ¹									
Inclusion/exclusion criteria		X								
Demographic data		X								
Medical history		X								
Physical examination		X			X	X	X	X	X	X
Vital signs		X	X	X	X	X	X	X	X	X
Pregnancy test ²		X		X	X	X	X	X	X	
Hematology, biochemistry & lipid panel ³		X			X	X	X	X	X	X
Urinalysis		X			X	X	X	X	X	X
Blood rapamycin concentration ^{3,4}		X			X	X	X	X	X	X
Drug administration (once daily, evenings)				X						
Photographs of FA			X		X	X	X	X	X	X
IGA		X	X		X	X	X	X	X	X
FASI			X		X	X	X	X	X	X
Percentage improvement (subjective & objective)					X	X	X	X	X	
Categorical improvement									X ⁵	
Concomitant medications		X	X	X						X
Adverse events				X						X

¹ if more than a month passes between obtaining informed consent and randomization, then informed consent should be re-obtained

² only conducted for women of childbearing potential

³ if participants are unable to provide blood samples at all timepoints, the minimum to be collected should be samples at screening, V1 or V2 and V5

⁴ blood sampling collected prior to the daily evening dose

⁵ categorical assessment only to be done at V5, unless early withdrawal/discontinuation, in which case categorical assessment should be completed at last visit

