7.1 Screening Phase

The screening phase will occur up to 3 months prior to the initial Clinical Visit (V0).

Prior to the initiation of the screening assessments, potential participants will be given a complete explanation of the study.

Informed Consent may be obtained up to 3 months prior to the initial Clinical Visit (V0), however if more than one month passes between obtaining informed consent and randomization, then informed consent should be re-obtained.

Once an individual has agreed to participate and signed a copy of the Informed Consent documents the following assessments will be performed up to 14 days prior to V0 to assess the participant's eligibility for enrolment in the study according to the Inclusion/Exclusion criteria:

- Demographic data (age, sex, height, weight etc.)
- Complete medical history - including past or present history of cardiac, pulmonary, gastrointestinal, hepatic, renal, immunological, hematological, neurological, musculoskeletal or psychiatric conditions (if any), allergy to food or drugs and medication history for the previous three months.
- Physical examination
- Vital signs (temperature, blood pressure [systolic and diastolic], pulse rate)
- Urine pregnancy tests (females of childbearing potential only)
- Hematology
 - Hemoglobin
 - Hematocrit
 - Platelet count
 - Red Blood Cell (RBC) count
 - White Blood Cell (WBC) count
 - Differential Leukocyte Count (DLC)
- Biochemistry
 - Sodium
 - Potassium
 - Urea
 - Creatinine
 - Phosphate
 - Glucose
 - Albumin
 - Total protein
 - Alkaline phosphatase

- Gamma-glutamyl transferase
- Aspartate transaminase
- Alanine transaminase
- Bilirubin
- Lipid panel
 - Total cholesterol
 - High-density lipid cholesterol
 - Low-density lipid cholesterol
 - Triglycerides
- Blood rapamycin concentration
- Urinalysis
- Clinical examination of FA lesions using the Investigators Global Assessment (IGA)
- Concomitant medications

If subjects meet all eligibility criteria, they will be assigned a unique randomization number up to two weeks before the first application of the study drug, at which time the following baseline assessments will be conducted:

- Vital signs (temperature, blood pressure [systolic and diastolic], pulse rate)
- Photographs of FA lesions
- Clinical examination of FA lesions using the Investigators Global Assessment (IGA) and Facial Angiofibroma Severity Index (FASI)
- Concomitant Medications

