10.3.2 Secondary Efficacy Endpoints

The time-to-treatment success will be summarized using Kaplan-Meier analyses and compared between each dose group and placebo using the stratified log-rank test. The secondary endpoints change in IGA and FASI from baseline to 26 weeks/last assessment, and objective and subject improvement from baseline to 26 weeks/last assessment, will be summarized by treatment group using means, medians, standard deviations, interquartile ranges and minima and maxima. These changes will be analyzed using ANOVA including treatment and stratum as main effect fixed factors, with planned pairwise comparisons between each dose group and placebo. If the data is not adequately normally distributed the Kruskal-Wallis non-parametric ANOVA, and Mann-Whitney U tests comparing changes between treatment groups will be used for the analysis. Baseline for the IGA and FASI scores is defined as the last pre-treatment assessment, whether obtained at screening, randomization or V0.

Categorical Improvement scores will be compared amongst study groups using the Kruskal-Wallis non-parametric ANOVA, and Mann-Whitney U tests comparing changes between each dose group and placebo.

The type I error rate associated with the testing of the six secondary endpoints will be strictly controlled using the Hochberg procedure. This will involve ranking the 6 p-values derived from the testing of each dose group with placebo from highest to lowest. If the highest p-value is <0.05 , then all six comparisons are considered statistically significant if not significant then the next highest is tested at $p=0.025$. The p-value continues to reduce at each non-significant step based on the Bonferroni adjustment.

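### Eligibility is checked against the screening IGA, but baseline is the later randomization IGA, which is not required to be 2 or 3; a patient re-graded to 1 can enter and cannot succeed

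*Combined protocol and SAP*

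**What the plan says.** **Entry range.** Section 4.2 requires "An FA severity score of 2 or 3 on the IGA scale". Section 4.3 excludes grade 4 and also "Patients with an FA severity score of less than 2 on the IGA scale". None of these criteria names a visit.

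**When it is checked.** Section 7.1 lists the IGA among the screening assessments, "performed up to 14 days prior to V0 to assess the participant's eligibility for enrolment in the study according to the Inclusion/Exclusion criteria". In the schedule (Table 3 and the synopsis), the row "Inclusion/exclusion criteria" has one mark, under Screening.

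**Second grading.** Section 7.1 continues: "If subjects meet all eligibility criteria, they will be assigned a unique randomization number up to two weeks before the first application". At that same point it calls for baseline assessments that include a second IGA. The schedule marks the IGA at Screening and at Randomization, and not at V0. Sections 5.3 and 7.2 also put confirmation of eligibility before randomization.

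**Baseline.** Section 10.3.2 states: "Baseline for the IGA and FASI scores is defined as the last pre-treatment assessment, whether obtained at screening, randomization or V0". The synopsis repeats this, and Section 10.3.1 gives no other definition for the primary endpoint.

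**Success and population.** Section 6.1.1 defines success as "clear or almost clear with an improvement of at least two grades from baseline". Under Section 10.1 the ITT population is everyone who receives at least one dose. Section 10.3.1 adjusts for baseline IGA.

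**The concern.** The grade that admits a patient and the grade from which the primary endpoint is measured are two separate readings, and only the first has a range attached. If they differ, the plan does not say what follows.

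The disease is unlikely to change within two weeks, so disagreement would come mainly from grading. The sponsor developed this scale. Section 10.2 says this is its first use for facial angiofibroma severity, and the documents report no reliability data for it. Its grades turn on words such as few and predominantly. A single grader per patient is asked for only as far as possible (Section 6.1.1).

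At stake are patients in the primary analysis who cannot succeed on any treatment, and patients whose baseline lies in a severity range the protocol excludes.

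**Working it through.** **1. Which grading is baseline.** Pre-treatment IGAs on the schedule are at Screening and Randomization, with none at V0. The last one is at Randomization.

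**2. Which final grades count as success.** The rule needs a final grade of 0 or 1 and a drop of at least 2.

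| Baseline | Final grades that succeed |
|---|---|
| 1 | none |
| 2 | 0 |
| 3 | 0, 1 |
| 4 | 0, 1 |

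From grade 1 the largest possible drop is one grade, so success is impossible in any arm. A re-grade from 3 to 4 leaves the successful final grades unchanged; there the issue is eligibility and the covariate range.

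**3. The plan's own sample size.** Section 10.2 gives 10% against 40%, alpha 0.025, more than 80% power and 40 per group. Sidedness is not stated; I take two-sided (z = 2.2414). With the pooled normal formula and mean rate 0.25:

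n = [2.2414 × √(2 × 0.25 × 0.75) + 0.8416 × √(0.10 × 0.90 + 0.40 × 0.60)]² / 0.30² = (1.3726 + 0.4835)² / 0.09 = 38.3, so 39.

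Power at 40 = Φ[(0.30 × √40 − 1.3726) / 0.5745] = Φ(0.914) = 82.0%. The stated 40 and >80% are reproduced. Exact power of the uncorrected chi-square test at 40 per group is 83.3%.

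**4. How many patients (assumed).** The documents give neither a re-grading rate nor the split of grades at entry. Assume 30-50% enter at grade 2, and 5-20% of patients shift one grade, half in each direction.

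- Baseline 1: from 0.30 × 0.05 / 2 = 0.75% to 0.50 × 0.20 / 2 = 5%.
- Baseline 1 or 4 together: from 0.05 / 2 = 2.5% to 0.20 / 2 = 10%, that is 3 to 12 of 120 patients.

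**5. Effect on power.** With a share q at baseline 1, both success rates are multiplied by (1 − q). At q = 5% they are 9.5% and 38.0%, so the difference falls from 30 to 28.5 percentage points. By the normal formula, power = Φ[(0.285 × √40 − 2.2414 × √(2 × 0.2375 × 0.7625)) / √(0.095 × 0.905 + 0.38 × 0.62)] = Φ(0.800) = 78.8%.

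| q (assumed) | Exact chi-square | Normal formula |
|---|---|---|
| 0 | 83.32% | 81.95% |
| 1% | 82.74% | 81.35% |
| 2.5% | 81.85% | 80.42% |
| 5% | 80.30% | 78.81% |

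The normal formula passes below 80% between q = 3% (80.10%) and q = 3.5% (79.78%), that is 1.2 to 1.4 patients per arm of 40. The exact chi-square figure stays above 80% at q = 5%. Both are unadjusted two-group calculations, not the planned logistic model.

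**The case against.** **The patient need not be randomized.** A reader might infer that the plan sends a patient re-graded to 1 into the trial. It does not say that. Criteria naming no visit can be applied to the second grade; Section 4.1 enrols only patients who meet all criteria; and the second IGA is done when the number is assigned, not clearly after it. This stands as a limit: such a patient can be randomized. But nothing requires a re-check, and the schedule and Section 7.1 place the check at screening, so sites could differ.

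**Randomization is not ITT entry.** ITT needs a dose, and the first dose is a separate supervised step at V0. An undosed patient would be replaced, because Section 5.3 enrols until at least 120 are randomized and have started study drug. This is correct, but no passage tells a site to act on an out-of-range randomization grade before V0.

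**Safeguards exist.** The per-protocol analysis drops major violations, results are shown by baseline IGA group, and one grader per patient is preferred. These help interpretation, but the ITT analysis remains primary.

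**The size rests on assumptions.** It does. Scaling by (1 − q) also assumes that grade-2 patients succeed at the average rate, although they must reach 0. If they succeed half as often as grade-3 patients (a further assumption), exact power at the 5% corner is 81.3%. Shifts between 2 and 3 are ignored.

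**The model could break down.** A reader might infer that a grade-1 level with no successes would cause separation in the logistic model. That happens only if baseline IGA is fitted in categories. Section 10.3.1 lists it as a covariate, apart from the fixed factors, and entered as a number it creates no empty level.

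**Conclusion.** The gap is real and small. The entry range is scheduled for checking on one grading, baseline is taken from another, and no text requires the second to be in range. A patient with a baseline of 1 who is dosed is a certain failure in the primary analysis.

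On an assumed 1-5% of patients at baseline 1, power loses up to about 3 percentage points: 83% to 83-80% by exact chi-square, 82% to 81-79% by the normal formula. Whether it drops below 80% depends on the formula and on a rate the documents do not give, so they do not support saying that the trial would be underpowered for this reason.

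Nor do they support a reading of bias toward active treatment. The second grading is pre-treatment and blinded, so out-of-range baselines are expected equally in each arm and the type I error rate is not inflated. The harm is dilution, plus a few patients outside the intended severity range. I would label this a cheap improvement.

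**What to change.** - In Sections 4.2 and 7.1 and in the schedule of assessments, require the IGA to be 2 or 3 at both screening and randomization.
- In Section 7.1, do the randomization IGA before the number is assigned, and assign the number only if that grade is in range.
- Reconcile Section 6.1.1, which lists IGA gradings at screening, V1-V5 and follow-up and omits the one at randomization. Reconcile also the baseline definition, which allows for a V0 grading that is not scheduled.

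This adds no visit and no assessment; it reorders steps within an existing one. The costs are a few extra screen failures and some incentive to grade into range at the reading that serves as baseline. That incentive already exists at the screening check, and grading is blinded.

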Although a range of concentrations appear to be effective, adults tended to have a poorer response to treatment than children for a given strength, suggesting the need for higher concentrations in this age group where FA are typically more severe (33,45,46). There is some data to suggest that higher concentrations have greater efficacy, particularly in adult patients (37,45). Moreover, most authors suggested the use of topical rapamycin at early stages (in younger patients) so optimal results can be achieved.

Table 1: Published Clinical Trials for Topical Rapamycin for Facial Angiofibroma

Study	Study Design	Strength	N	Frequency and Duration of therapy	Efficacy
Wataya-Kaneda et al., 2018	Multicenter, double-blind, randomized, placebo-controlled, parallel group	0.2%	62	2x daily for 12 weeks	
Primary endpoint: composite improvement in angiofibromas (size and color at 12 weeks). Response rate of angiofibromas at weeks 4, 8, and 12 of treatment was 0 in the placebo group in contrast to 20%, 43% and 60% in the rapamycin group. None of the 31 assessable patients in placebo group were rated improved or better and 26 of them were rated unchanged. In contrast 17% and 43% patients in the rapamycin group were rated “markedly improved” and “improved”, respectively.
 
In the rapamycin group the response rates were significantly higher in the pediatric patients (85%) than in adult patients (41%) at week 12 (p=0.03)
 
Rapamycin gel, 0.2% demonstrated a significant clinical benefit for patients with TSC involving angiofibromas, thus providing a promising therapeutic modality.

Koenig et al., 2018	Multicenter, double-blind, randomized, vehicle-controlled, parallel group	0.1% 1%	179	1x daily at bed time for 6 months	
Clinically meaningful and statistically significant improvement in facial angiofibroma was observed for both 1% and 0.1%. At 6 months, Angiofibroma Grading Scale (AGS) mean improvement for 1% was 16.7 points compared with 11.0 for 0.1% and 2.1 points for vehicle only (P<0.001 for 1% and 0.1% vs vehicle only). End-of-treatment photos were rated “better” for 81.8% of patients in the 1% rapamycin group, compared with 65.5% for those in the 0.1% rapamycin group and 25.5% for those in the vehicle-only group (P<0.001, all 3 pairwise comparisons).
 
Topical rapamycin was generally well-tolerated with no measurable systemic absorption.

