5.3 Randomization

Randomization will occur at the study site once participant eligibility is confirmed, up to two weeks before the first clinical visit (V0), which includes the first application of the study drug. Participants

will be randomly assigned to one of three possible treatments in a balanced fashion (i.e. 1:1:1 ratio). Each successive subject will receive a unique study randomization number which includes both a two-digit site prefix (e.g. 01), a single-digit age stratum identifier (e.g. 0) and two-digit subject identifier (e.g. 01). For example, the first patient in the first stratum (age group: 6 – 11 years) at site #1 will be assigned the randomization number 01-001. Randomization will be balanced by using permuted blocks and stratified by site and age group (6 – 11 years; 12 – 17 years; 18 – 65 years). Participants will be enrolled into the study until a minimum of 120 participants are randomized and have started using study drug.

The randomization sequence will be computer-generated by the study statistician prior to any enrolment. The statistician will maintain a confidential schedule of participant IDs and treatment allocations. The dispensing pharmacist at each site will not be blinded, and will maintain a confidential schedule of participant IDs and treatment allocations for participants at their site. The pharmacist will be responsible for over-labelling the study medication. The randomization sequences will be maintained by the site pharmacist in a secure location which cannot be accessed by other staff members involved in the conduct of the trial.

The sites will receive a set of sealed blinding envelopes for emergency un-blinding, with a separate envelope for each participant number. The principal investigator will be the first point of contact should the randomization code need to be broken for an individual participant during the study. The emergency unblinding envelopes for each participant should only be opened in an emergency when knowledge of the study drug may affect the management of the patient.

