10.3 Statistical Analyses

10.3.1 Primary Efficacy Endpoint

The data for the primary endpoint, the percentage of patients obtaining successful treatment based on the blind assessment using the IGA scale after 26 weeks or at last visit if early withdrawal/discontinuation, will be summarized by treatment group. Success is defined as clear or almost clear with an improvement of at least two grades from baseline, i.e. 2 to 0; 3 to 1. Statistical analysis of the primary endpoint will be performed using a logistic regression model which will include treatment effect and stratum as fixed factors and baseline IGA score as a covariate. This model will be used to generate the odds ratios and 95% confidence intervals of the individual dose treatments compared with placebo, with the p-values for these comparisons adjusted using the Holm-Bonferroni adjustment.

An exploratory analysis will compare the two active groups in the same manner as the primary endpoint, with no adjustment for multiple comparisons. This analysis will be summarized with the Odds ratio and 95% confidence interval.

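### The rank tests for Categorical Improvement, and the non-normality fallback for four other secondary endpoints, omit the stratum that the other efficacy analyses keep

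*Combined protocol and SAP*

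**What the plan says.** Section 5.3: "Randomization will be balanced by using permuted blocks and stratified by site and age group", with three age groups (6-11, 12-17 and 18-65 years). The randomization number has a site prefix, then "a single-digit age stratum identifier (e.g. 0) and two-digit subject identifier". So the word stratum is attached to age there, although the randomization itself uses both factors.

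Three analyses carry a stratum:

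- Primary endpoint (Section 10.3.1): "a logistic regression model which will include treatment effect and stratum as fixed factors".
- Time to treatment success (Section 10.3.2): "compared between each dose group and placebo using the stratified log-rank test".
- Change in IGA, change in FASI, and the subjective and objective ratings (Section 10.3.2): "These changes will be analyzed using ANOVA including treatment and stratum as main effect fixed factors".

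Two do not, both in Section 10.3.2 and repeated in the synopsis:

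- Categorical Improvement: "Categorical Improvement scores will be compared amongst study groups using the Kruskal-Wallis non-parametric ANOVA, and Mann-Whitney U tests". These are its only planned tests.
- The fallback for the four ANOVA endpoints: "If the data is not adequately normally distributed the Kruskal-Wallis non-parametric ANOVA, and Mann-Whitney U tests".

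No other section adds stratification to the rank tests or says why it is left out.

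**The concern.** A test that ignores a factor used in the randomization remains valid. If that factor also predicts outcome in every arm, though, the test counts between-stratum spread as noise. It then rejects less often than its nominal level under the null and has less power under the alternative.

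Categorical Improvement is certain to be affected. The other four endpoints are affected only if the fallback is triggered. That could happen: baseline IGA is 2 or 3 on a 0-4 scale, so change in IGA takes few integer values, and no criterion for adequate normality is given. An endpoint would then move from a stratum-adjusted to an unadjusted analysis.

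There is one design reason to expect an age difference in all arms. Section 6.1.2 and Appendix 4 have the parent or caregiver rate Categorical Improvement, and the subjective rating, for patients under 18. That cut-off is also the boundary between the 12-17 and 18-65 strata. The documents give neither the size nor the direction of any rater effect. It would not apply to IGA, scored by a blinded dermatologist, or to the objective rating, made by the investigator.

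The six secondary endpoints share one Hochberg family, so an inefficient test of one can tighten the threshold the others face.

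**Working it through.** **The plan's own figure.** The documents give no power for the rank tests. For the primary endpoint (10% vs 40%, two-sided alpha 0.025) the normal-approximation formula gives 39 per group, and 40 per group gives power 0.82. This agrees with the stated 40 per group and power above 80%, and the present point does not alter it.

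**Tests compared.** Within stratum k, with n_k patients (n_1k active, n_0k placebo) and midranks r:

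- W_k = sum of active ranks; E_k = n_1k(n_k + 1)/2
- V_k = [n_1k n_0k / (n_k(n_k − 1))] × Σ(r − r̄)²
- Mann-Whitney: one stratum, z = (W − E)/√V
- van Elteren: w_k = 1/(n_k + 1), z = Σ w_k(W_k − E_k) / √(Σ w_k² V_k)

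**Inputs from the documents.** 40 per group; five ordered categories (Appendix 4); three age groups (Section 5.3).

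**Assumed inputs.** A latent normal outcome cut into five categories; 12/8/20 patients per arm aged 6-11/12-17/18-65; effects of 0.6, 0.8 and 1.03 SD; age gaps of 0 to 1.0 SD. The 1.03 is the probit distance of the planned primary rates, Φ⁻¹(0.40) − Φ⁻¹(0.10) = −0.253 + 1.282 = 1.03, carried over by assumption. The age gap is either a child/adult step or graded over the three groups. Each scenario had 40,000 replicates at two-sided 0.05.

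**Age prognostic in all arms, effect 0.6 SD (power, %)**

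| Age gap (SD) | Step: Mann-Whitney | Step: van Elteren | Graded: Mann-Whitney | Graded: van Elteren |
|---|---|---|---|---|
| 0.5 | 68.8 | 70.4 | 68.9 | 70.0 |
| 0.75 | 65.6 | 69.9 | 67.0 | 69.8 |
| 1.0 | 61.4 | 69.3 | 64.1 | 69.8 |

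By subtraction, Mann-Whitney loses 1.1-1.6 points at a gap of 0.5, 2.8-4.3 at 0.75 and 5.7-7.9 at 1.0. Break-even is at a gap of about 0.25-0.3 SD. At an effect of 0.8 SD the loss is 0.4-4.2 points; at 1.03 SD it is about 1 point or less.

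**Type I error (nominal 5%).** Mann-Whitney: 4.4-4.5% at gap 0.5, 3.7-3.9% at 0.75, 2.9-3.3% at 1.0. van Elteren: 4.8-5.0%.

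**When age is not prognostic.** With no age effect, van Elteren costs 0.1-0.5 points. If age only modifies the drug effect, it costs 0.6-1.6 points at 0.6 SD and 0.3 or less at 1.03 SD.

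**With the actual randomization scheme.** 120 patients, permuted blocks within site-by-age cells, 12 sites and three age mixes assumed, effect 0.6 SD. Age-stratified van Elteren changes power by −0.3 to +1.3 points at a prognostic gap of 0.5 and by +3.7 to +7.8 at 1.0. It costs 0.5-1.1 points with no age effect, and 0.5-3.4 if age only modifies the drug effect (worst with 70% adults).

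**Age alone or site-by-age.** Stratifying the rank test by site-by-age cell gives power 10-24 points below stratifying by age. A separate simulation (age mix 25/25/50%, graded age gap of 1.0 SD, effect 0.6 SD) gave 0.64, 0.59, 0.54 and 0.47 with 5, 10, 15 and 20 sites, against 0.67-0.69 by age alone.

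**The case against.** The strongest reply is that no error is alleged and that the documents' own age evidence points away from a gain. Section 1.2 says that "adults tended to have a poorer response to treatment than children for a given strength", and the 85% vs 41% contrast in Table 1 is within a rapamycin group. Both concern treated patients, so they are closest to the case where age modifies the drug effect and stratifying costs a little. In the same cited trial, none of 31 placebo patients was rated improved or better and 26 were unchanged, which leaves little placebo spread for age to explain (a different scale, at 12 weeks).

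The effect may also be larger than 0.6 SD. Table 1 reports end-of-treatment photographs rated better in 81.8% (1%), 65.5% (0.1%) and 25.5% (vehicle) of patients. The probit distances from vehicle are 0.91 + 0.66 = 1.57 and 0.40 + 0.66 = 1.06 SD. At 1.06 SD, Mann-Whitney and van Elteren have power 99.1% and 99.2% (age gap 0.5), and 98.6% and 99.1% (gap 1.0). At the strictest Hochberg level, 0.05/6 = 0.0083, the loss at 1.06 SD is about 4 points for a gap of 1.0 and 0.5 points for a gap of 0.5.

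Finally, if stratum in the other analyses means site-by-age, an age-only rank test would not match them.

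All of this stands as a limit on the benefit. It does not change the reading of the text: the rank tests omit a stratum that the other analyses keep, without explanation. The doubt about what stratum means is a reason to define it.

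**Conclusion.** The point holds, as something to consider and not as an error to correct. The unstratified rank tests are valid, and the primary endpoint and sample size are unaffected. One secondary endpoint is certain to be analysed without the stratum, and four more would be if the fallback is used.

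The gain from stratifying by age is conditional. At an effect of 0.6 SD it is about 1-2 points at an all-arm age gap of 0.5 SD, 3-4 at 0.75 and 6-8 at 1.0. It is nil below about 0.25-0.3 SD, and about 1 point or less at an effect near 1 SD at the 0.05 level. The possible cost is about 0-3.4 points. The effect sizes, age gaps, age mix and number of sites are all assumed, and the documents do not show that age predicts outcome on placebo. The main reason for the edit is therefore consistency: these tests should use the age group the trial already randomizes by.

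**What to change.** In Section 10.3.2 and the synopsis, replace the pairwise Mann-Whitney tests, for Categorical Improvement and wherever the non-parametric fallback applies, with: van Elteren tests of each dose group against placebo, stratified by age group (6-11, 12-17, 18-65 years). If an overall Kruskal-Wallis test is kept, stratify it the same way, using the Cochran-Mantel-Haenszel row-mean-scores test with modified ridit scores.

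State that the stratum for these tests is age group alone, in line with the age stratum identifier in Section 5.3, because site-by-age cells are too sparse with 120 patients. It would help to say in the same place what stratum means in the logistic, log-rank and ANOVA analyses.

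The change is to wording only and uses standard software. Its one statistical downside is the 0-3.4 points of power given above if age is not prognostic or only modifies the drug effect. It should be made before unblinding.
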